12. WITHDRAWAL OF SUBJECTS

Participants can stop their participation at any time. Participants may refuse to answer any question and they may leave the study at any time.

13. RISKS TO SUBJECTS

For the survey portion of the study, involvement in this study does not involve any physical risk. The possible risks might be feeling uncomfortable answering questions.

There are no known risks associated with providing a urine sample other than a potential loss of confidentiality.

14. POTENTIAL BENEFITS TO SUBJECTS

Participants in the intervention and feasibility scale-up pilot may benefit from study participation by improving dietary habits and/or reducing bladder cancer recurrence. The information gained may also help other bladder cancer patients in the future. Participants will receive \$100 for completing each assessment—the study will ask participants to complete baseline (see Appendix

F) and 6-month follow-up assessments (See Appendix G1). Thus, participants will be able to receive up to \$200 total in assessments. Participating physicians will receive \$100 for the interview.

15. DATA AND SPECIMEN BANKING

All questionnaire data will be stored in REDCap or in a locked file cabinet. REDCap is a secure application supported by Partners Research Computing, Enterprise Research Infrastructure & Services (ERIS). ERIS has all the necessary physical and operational securities in place to meet or exceed Federal and State security and privacy regulations for data transmission and storage using REDCap. Data will only be removed when coded, entered, or audited. The urine samples will be processed and stored at [name] laboratory and a dataset will be created to track and record the results obtained from laboratory assays on urine samples. The dataset will only contain study IDs without any personal identifiable information. The file that contains the link between study ID and subject identifiable information will be maintained separately and can only be accessed by Drs. [name] and [name] and will never be released to any laboratory staff.

16. MEASUREMENT OF EFFECT

Solid Tumors

N/A

Hematologic Tumors

N/A

Other Response Parameters

We will assess the treatment intervention's effect on the consumption of cruciferae vegetables and ITC yield, as specified under the heading, "STUDY ENDPOINTS". We will also assess changes in gene expression via RNA-Seq, so as to identify a panel of genes that respond specifically to consumption of cruciferae vegetables as specified in the section of STUDY ENDPOINTS. It is well known that isothiocyanates in cruciferae vegetables alter multiple signaling pathways. Therefore, the identified panel of genes can be used as biological biomarkers to understand how individuals respond to the consumption of cruciferae vegetables, and more importantly, be used as biomarkers to monitor the effect of cruciferae vegetables.

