
Control intervention. Participants in the control arm will receive mailed materials about general fruit and vegetable intake intervention based on published NCI guidelines. (<https://cancercontrol.cancer.gov/ocs/>). The control intervention will utilize the same delivery method (i.e. mailed educational materials, live phone call, IVR calls) and follow the same contact schedule as the treatment schedule (See Appendix P and Appendix Q). We intend to compare our tailored cruciferae program with general program on increase of fruit and vegetable intake. We anticipate minimal contamination between intervention and control because BCS will be recruited throughout our catchment area and our intervention will be delivered individually with each BCS.

Personnel Training. [name] will utilize her extensive experience in training others in the delivery of behavioral interventions to train project staff to implement the intervention. A training-of-trainers model that incorporates didactic education, trainee practice, and written and verbal feedback will be used. Training will build knowledge about behavior change promotion, with a specific emphasis on delivering the live phone call with fidelity, utilizing participant booklets to program the IVR messages, and communicating effectively with participants about health. The training will conclude with project staff demonstrating mastery of concepts through mock phone sessions and live phone calls, and accurate programming based on booklet data received. Project staff will be asked to complete a checklist of topics to monitor intervention fidelity.

Aim 2: Conduct a feasibility pilot of our evidence-based dietary behavioral intervention

Study Design. We will use a Hybrid I implementation randomized-controlled design to simultaneously gather outcomes regarding the intervention's feasibility and process data to facilitate wide-spread implementation and dissemination of the intervention into clinical practice if the intervention is effective. A total of 80 patients will be recruited on a rolling basis. Forty will be randomized to intervention and 40 to control.

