For primary analysis, the aim is to investigate the between-group differences in the change of urinary ITC levels and cruciferae intake between baseline and post-intervention. The comparison of change from baseline will be made utilizing analysis of covariance (ANCOVA) and F-tests ($\alpha=0.05$). The intervention group will be used as factors and the baseline variables used as covariates. A coefficient for interventional group that is significantly greater than 0 will indicate that the intervention increases the ITC levels or cruciferae intake. Within-group difference between two time-points will be compared by two-sided paired sample t-tests, while between-group difference at each time-point will be compared by two-sided independent sample t-tests ($\alpha=0.05$). Since this is a pilot feasibility study, no adjustment for multiple comparisons will be planned.

Secondary Analyses.

The aim of secondary analysis is to investigate the difference in gene expression patterns between two groups. Three urine samples per participant will be collected at baseline and month 6, and the cell pellets from three urine samples per participants will be combined and subject to RNA-seq. RNA-seq data will be processed and quality-checked by Bioinformatics Shared Resource at Roswell Park; sample relationships will be explored using sample clustering and principle component analysis. We will use DESeq to identify significantly differentially expressed (SDE) genes and conduct pathway analysis with GSEA using rank-based gene list from SDE analysis. All tests will be two-sided at significance level of 0.05. We will use the Benjamini-Hochberg's method to calculate the false discovery rate (FDR) for gene expression.

The additional metabolites and biomarkers will be analyzed using the same approach as in primary analysis. The univariate distributions of these variables will be examined, and appropriate transformations may be applied before analysis. Benjamini-Hochberg's method to control the FDR.

Exploratory Analysis.

Qualitative methodology using content analysis will be used to ascertain physician barriers and facilitators to the intervention's implementation within clinic settings.

Safety Analysis

N/A

Interim Analysis

None

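### The RNA-seq contrast between two active diet programs cannot show that genes respond specifically to cruciferae or can serve as monitoring biomarkers

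*Combined protocol and SAP*

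**What the plan says.** Section 16 (Measurement of Effect, Other Response Parameters) gives the purpose of the RNA-seq work: "so as to identify a panel of genes that respond specifically to consumption of cruciferae vegetables". It reasons that ITCs are known to act on several signaling pathways, and from this infers that the panel can help explain individual responses and can "be used as biomarkers to monitor the effect of cruciferae vegetables". It refers to section 8 (Study Endpoints) for detail. Section 8 gives gene expression a surrogate role for efficacy, but defines no panel, no criterion for specificity and no validation step.

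Section 19 (Statistical Plan, Secondary Analyses) is more modest: "The aim of secondary analysis is to investigate the difference in gene expression patterns between two groups". The gene-level work is a DESeq comparison followed by pathway analysis on the ranked genes. Testing is two-sided at the 0.05 level, and on multiplicity the section says: "We will use the Benjamini-Hochberg's method to calculate the false discovery rate (FDR) for gene expression".

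Section 11 (Control intervention) describes the comparator: "Participants in the control arm will receive mailed materials about general fruit and vegetable intake intervention based on published NCI guidelines". Delivery method and contact schedule match those of the cruciferae arm.

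**The concern.** Section 16 makes a claim about a food: these genes respond to cruciferae and not to something else. Section 19 answers a question about assignment: which genes differ between people given one program and people given the other. The two coincide only if the programs differ in nothing but cruciferae intake, and here they differ in more than that.

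- The control call script (Appendix Q) sets a goal of 4-5 cups of fruit and vegetables a day. The cruciferae arm's goal is one serving of cruciferae a day (section 10, Appendix P).
- The cruciferae arm is also advised on choice of vegetable, cooking method and eating at dinner or later (Appendix P).
- The control magazine lists cabbage, cauliflower, Brussels sprouts and broccoli among common vegetables, so some cruciferae response may occur in controls too.

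Urinary ITC and cruciferae intake are measured at the same two time points as expression, but no planned model connects them to it. No hold-out sample or replication is planned. At stake is what the trial may conclude from its secondary outcome: a list of genes that differ between programs could be presented as a cruciferae-specific monitoring panel.

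**Working it through.** **1. The plan's own figure.** Inputs from section 19 (Sample Size Determination): 40 per arm, R² = 0.2, detectable difference 0.57 SD, 80% power. Alpha is 0.05, two-sided.

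- Standard error of the adjusted arm difference, in SD units: √(1−0.2) × √(2/40) = √0.04 = 0.20.
- 0.57/0.20 = 2.85, so power is Φ(2.85 − 1.96) = Φ(0.89) = 0.81. A noncentral t with 77 df gives 0.80.

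The stated 80% reproduces. It applies to the primary outcomes; no power figure is given for RNA-seq.

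**2. A gene with no cruciferae response.** The same standard error is used with a normal approximation in place of DESeq. The documents give no gene-level effect sizes, so the shifts are assumptions shown as a range. The p<0.001 column stands in for a stricter, FDR-like cut-off.

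| Shift caused only by the control program | Shift/0.20 | P(flagged), p<0.05 | P(flagged), p<0.001 |
|---|---|---|---|
| 0.3 SD | 1.50 | 0.32 | 0.04 |
| 0.57 SD | 2.85 | 0.81 | 0.33 |
| 1.0 SD | 5.00 | 0.999 | 0.96 |

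A gene moved by the same amount by cruciferae in the intervention arm has identical probabilities, so the contrast cannot separate the two. Benjamini-Hochberg limits the share of genes with no arm difference at all. A fruit-driven gene does have an arm difference, so it is not a false discovery in that sense.

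**3. A true cruciferae gene, diluted.** Take a 0.57 SD response and let controls attain a fraction f of it. The contrast becomes 0.57(1−f).

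| f | Power, p<0.05 |
|---|---|
| 0 | 0.81 |
| 0.25 | 0.57 |
| 0.50 | 0.30 |
| 0.75 | 0.11 |

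This is lost power; it does not create false specificity.

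**4. What an added ITC model must contain.** I simulated 40 per arm and a gene that responds to fruit only. Assumptions: changes in fruit and cruciferae independent with SD 1; each program raises its own target by 0.8 SD; gene-on-fruit slope 0.8 with residual SD 1; ITC-cruciferae correlation 0.3, 0.5 or 0.7; intake measured without error. The expected arm difference is 0.8 × 0.8 = 0.64, with standard error √(0.64+1) × √(2/40) = 0.286, so about 61% of such genes are flagged at p<0.05. Of those flagged:

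| Covariate and rule for the ITC slope | Share that also pass |
|---|---|
| Total fruit and vegetables, same sign only | 82%, 95%, 99% (correlation 0.3, 0.5, 0.7) |
| Non-cruciferous intake, same sign only | about 50% |
| Non-cruciferous intake, same sign and p<0.05 | 2-3% |

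Total intake contains cruciferae. With arm and total held fixed, higher ITC implies less fruit, so a fruit gene acquires an ITC slope in the same direction as its arm contrast. The covariate must therefore exclude cruciferae, and the slope must pass a threshold of its own.

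**The case against.** The strongest defense is that the comparison is randomized and contact-matched. The arm contrast is a valid estimate of the effect of one program against the other, and the active control removes attention effects and part of general dietary change. That stands, and it helps specificity. It does not settle which component of which program moved a gene.

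A second defense is that RNA-seq is run at baseline and month 6 in both arms, and that section 19 plans within-arm summaries of change in general terms. Applied to expression, these would show which arm moved. But the plan does not specify them for RNA-seq, and a change within the intervention arm would still not isolate cruciferae.

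Third, this is a secondary outcome in a feasibility pilot, where the lack of a validation sample is normal. That is fair, and it argues for candidate language, which section 16 does not use.

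A reader might infer stronger points that the documents do not support:

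- *Every gene moved by the control program will enter the panel.* No. It must reach significance, and a 0.3 SD gene does so with probability 0.32 at p<0.05 and 0.04 at p<0.001.
- *The panel is the trial's efficacy surrogate.* Sections 1 and 8 give that role to gene expression, not to a panel.
- *The trial will declare a usable panel.* Section 19 has no rule that does so; the claim appears only in section 16.
- *Intervention participants who did not change, and controls who ate cruciferae, create false specificity.* They dilute the contrast. Leaving them in is ordinary analysis by assigned arm.

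**Conclusion.** The concern holds for what section 16 says may be concluded. The planned contrast supports a statement that genes differ between two diet programs. It does not support specificity to cruciferae, and monitoring use would further need a within-person relation to intake or ITC and independent confirmation, neither of which is planned.

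The number of genes affected cannot be derived, because the documents give no gene-level effects or dispersion. What can be shown is that, under the plan's sample size and R² and a normal approximation, control-driven and cruciferae-driven genes of equal size are flagged equally often. The issue is worth correcting because it changes the permissible conclusion of the secondary outcome. It does not touch the primary analysis or the sample size.

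**What to change.** 1. **Section 16.** Replace the specificity claim and the statements that the panel can be used as biomarkers with: *genes that differ between the two programs and are candidates needing validation in an independent sample*.

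2. **Section 19, Secondary Analyses.** Add a supportive, observational model in all participants with paired samples. Regress change in expression (6 months minus baseline) on change in log creatinine-adjusted urinary ITC, adjusted for arm and for change in non-cruciferous fruit and vegetable intake from the 24-hour recalls. Describe a gene as a cruciferae-responsive candidate only if it passes the arm contrast and its ITC slope has the same sign and passes its own Benjamini-Hochberg threshold at 5%.

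No new data are needed: expression and ITC come from the same urine collections, and the recalls are taken at both assessments. The cost is some additional analysis, fewer genes and a weaker claim. The ITC slope is also not a randomized comparison. Urinary ITC reflects recent intake, cooking and timing, which the intervention itself changes, and three recalls measure intake with error. The slope can support specificity but cannot prove it, and the text should say so.

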17. SAFETY EVALUATION

Reporting Unanticipated Problems.

Unanticipated problem reporting will begin at the time of participant consent. The Reportable New Information (RNI) Form will be submitted to the Roswell Park Clinical Research Service (CRS) Quality Assurance (QA) Office within 1 business day of becoming aware of the Unanticipated Problem. After review, CRS QA Office will submit the RNI to the IRB.

When becoming aware of new information about an Unanticipated Problem, the updated information will be submitted to the CRS QA Office with an updated RNI Form. The site Investigator or designated research personnel will report all unanticipated problems to the IRB in accordance with their local institutional guidelines.

19. STATISTICAL PLAN

Patient. We will use SAS for data analysis and R for RNA-seq data. We will generate descriptive statistics and assess group differences at baseline and examine treatment drop-out and missing data patterns' impact on treatment effects. We will calculate summary statistics and compare study endpoints and patient baseline characteristics by treatment group using independent sample *t*-tests and Fisher's exact tests. We will summarize changes between pre- and post-intervention for both arms and calculate point estimates and their corresponding 95% confidence intervals. We will analyze between-group differences in the change of outcome variables between baseline and post-intervention using analysis of covariance (ANCOVA). The intervention group will be used as factors and the baseline variables used as covariates. Within-group difference between two time-points will be compared by paired sample *t*-tests, while between-group differences at each time-point will be compared by independent sample *t*-tests or Wilcoxon rank sum tests. RNA-seq data will be processed and quality-checked by the Bioinformatics Shared Resource at Roswell Park; sample relationships will be explored using sample clustering and principle component analysis. We will use DESeq258 to identify significantly differentially expressed (SDE) genes and conduct pathway analysis with GSEA59 using rank-based gene list from SDE analysis. All tests will be two-sided at the significance level of 0.05. We will use the Benjamini-Hochberg's method to calculate the false discovery rate for gene expression.

Physician. Interviews will be audio-recorded, transcribed verbatim, checked for accuracy and entered into a software program for the management of text data (e.g. NVivo 12). We will code transcripts using content analysis. Coding decisions and emergent findings will be discussed until an agreement is reached⁵⁷.

Sample Size Determination

Patient: With n=40 for each group, the ANCOVA can achieve 80% power to detect a difference of 0.57 within-group standard deviations (SDs) between groups assuming the correlation of post-intervention and baseline outcome is R²=0.2. Data from the Be-Well study reports a within-group SD of 8.9 μ M for urinary ITCs and 62 g/day for cruciferae intake; thus, we can detect a difference equivalent to 5.1 μ M in urinary ITC and 35.3 g/day of cruciferae intake between groups. The intervention's goal is to increase urinary ITC levels from the baseline of 4.4 μ M to the desirable biological dose of 10 μ M and cruciferae intake from the baseline of 52.7 gram (0.7 serving) to at least 75 gram (a typical serving size) at 6-month follow up. Given the generally lower cruciferae intake observed in other BCS studies (around 0.44-0.45 serving, equivalent to 33-34 gram per day)^{11, 26}, the proposed study will have sufficient power to detect our projected differences.

Physician: We will recruit up to 20 physicians to ensure data saturation⁶¹. Among clinicians involved in cancer treatment, enrollment rates between 46.3%-92% have been reported^{60, 62, 63}, with one study reporting an enrollment rate of 48% among clinicians involved in bladder cancer treatment⁶². Out of the 80 participants enrolled in our intervention, we anticipate 40 to nominate their physicians and expect to receive referrals for 5 additional physicians from enrolled physicians and 5 physicians nominated by our CAB. Given an anticipated enrollment rate of 48%, we anticipate recruitment of 20 physicians.

Randomization

Subjects will be randomized in a 1:1 fashion to the control arm and interventional arm using permuted block randomization. We will employ random block sizes of 4 and 2. Randomization will be carried out by the Department of Biostatistics and Bioinformatics.

Demographics and Baseline Characteristics

Descriptive statistics (as appropriate: n, percent, mean, median, min and max) will be used to summarize demographic and baseline characteristics. The patient characteristics will also be summarized by treatment group. The baseline characteristics between groups will be compared by independent sample t-tests and Fisher's exact tests as appropriate.

Primary Analysis.

For primary analysis, the aim is to investigate the between-group differences in the change of urinary ITC levels and cruciferae intake between baseline and post-intervention. The comparison of change from baseline will be made utilizing analysis of covariance (ANCOVA) and F-tests ($\alpha=0.05$). The intervention group will be used as factors and the baseline variables used as covariates. A coefficient for interventional group that is significantly greater than 0 will indicate that the intervention increases the ITC levels or cruciferae intake. Within-group difference between two time-points will be compared by two-sided paired sample t-tests, while between-group difference at each time-point will be compared by two-sided independent sample t-tests ($\alpha=0.05$). Since this is a pilot feasibility study, no adjustment for multiple comparisons will be planned.

Secondary Analyses.

The aim of secondary analysis is to investigate the difference in gene expression patterns between two groups. Three urine samples per participant will be collected at baseline and month 6, and the cell pellets from three urine samples per participants will be combined and subject to RNA-seq. RNA-seq data will be processed and quality-checked by Bioinformatics Shared Resource at Roswell Park; sample relationships will be explored using sample clustering and principle component analysis. We will use DESeq to identify significantly differentially expressed (SDE) genes and conduct pathway analysis with GSEA using rank-based gene list from SDE analysis. All tests will be two-sided at significance level of 0.05. We will use the Benjamini-Hochberg's method to calculate the false discovery rate (FDR) for gene expression.

The additional metabolites and biomarkers will be analyzed using the same approach as in primary analysis. The univariate distributions of these variables will be examined, and appropriate transformations may be applied before analysis. Benjamini-Hochberg's method to control the FDR.

Exploratory Analysis.

Qualitative methodology using content analysis will be used to ascertain physician barriers and facilitators to the intervention's implementation within clinic settings.

Safety Analysis

N/A

Interim Analysis

None

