Low cruciferae intake in bladder cancer survivors (BCS). Although the potential beneficial effect of dietary ITCs in bladder cancer is compelling, the consumption of the primary dietary resource of ITCs—cruciferae—is generally low among BCS. An average of 0.45 serving per day was observed in our retrospective study¹², similar to the report of the daily consumption of 0.44 servings in a pilot study of 48 BCS²⁶. Preliminary analysis of food frequency questionnaire (FFQ) data from over 1,400 newly diagnosed NMIBC patients from our Be-Well study (R01CA172855)²⁷ reported that daily intake of cruciferae was about 52.7 gram, or approximately 0.7 servings; while urinary ITC level was around 4.4 µM, which is below the averagely 10 µM of ITCs observed to stop or kill at least 50% of bladder cancer cells in *in vitro* models^{15, 17}. Based on our recent findings on the diverse range of ITC yield from cruciferae and the various impact of cooking methods on the ITC yield^{28, 29}, we believe that at least one serving (~1 cup raw or ½ cup cooked) of cruciferae per day, with guidance on the choice of vegetables and cooking conditions, will increase urinary ITC levels to the desirable doses needed to exert anti-cancer activities in the bladder.

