10. TREATMENT

The planned evidence-based behavioral intervention using techniques associated with effective dietary change in older adults (Table 1): problem solving, plan social support, goal setting, follow-up prompts, and provide feedback. The 6-month intervention will likely consist of the following, although aspects of the intervention may change based on data from the adaptation process: 1) Mailed educational materials about the importance of consuming cruciferae, how to maximize urinary ITC levels, serving size goals, the importance of self-monitoring, and strategies to increase intake, along with booklets to record daily cruciferae intake; 2) One live phone call (~45-60 minutes) delivered two weeks after mailing materials to verify understanding of the educational information and help participants complete a personalized action plan where participants will identify barriers and facilitators (e.g. social support) to meet identified goals (problem solving); 3) 11 Interactive Voice Response (IVR) phone messages that will begin by asking participants to input the servings of cruciferae consumed the previous week (follow-up prompt). Depending on number of servings participants input, they will be routed to one of three paths: a) meeting goals, b) not meeting goals but has some progress, c) no progress. Participants on each path will receive a tailored phone message (provision of feedback) selected from a library of messages to enable participants to meet or maintain their cruciferae goal. A total of 11 IVR calls will be delivered weekly for the first three weeks and then bi-weekly for the remainder of the 6-month intervention.

Table 1. Intervention Components

Intervention component	Intervention content/ behavior technique	SCT Construct	CAB adaptation
Educational Materials	
 Relationships between cruciferae, ITC yield, and bladder cancer Type of vegetable, cooking methods, and timing of intake for maximum ITC exposure Program goal of 1 serving of cruciferae per day/Goal setting Keeping track of servings eaten per day 	
 Knowledge Outcome expectations Behavioral skills Barriers and opportunities Intentions 	
 Barriers and facilitators to meeting goals, examples from BCS day-to-day life, strategies to meet goals, visuals pleasing to BCS

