Choose power vegetables with medium to high isothiocyanates, such as arugula, broccoli, broccoli sprouts, cabbage, mustard greens, water cress, daikon, or turnip.

How many power vegetables should I eat?

Eat at least one serving of power vegetables per day. One serving size is 1 cup at the time you eat it. So if you have a salad with arugula, it would be 1 cup raw. If you cook the arugula, it would 1 cup cooked. 1 cup is about the size of your fist.

6 POW-R HEALTH: Power to Redefine Your Health

RECIPES

Sautéed Greens

These sautéed greens are a breeze to make on your stove top. A little chopping and a few ingredients like garlic and tamari or soy sauce are all it takes. It's a great way to eat more greens!

Servings: 2 people
Prep Time: 10 minutes
Cook Time: 10 minutes

INGREDIENTS

2 bunches Swiss chard or other greens, roughly chopped
3 cloves garlic, chopped
1 tsp. low-sodium tamari or soy sauce (or to your liking)

INSTRUCTIONS

- Water sauté the chopped garlic for a few minutes. Then add the chopped stems and a little water and sauté a few minutes. Then add the rest of the greens.
- Continue sautéing the greens, turning frequently. Add more water if it dries out.
- Add the tamari or soy sauce to your taste and continue to sauté until softened, about 10 minutes.
- Serve with whole grains such as brown rice or quinoa, adding more soy sauce as needed.

Source: plantbasedcooking.com

POW-R HEALTH: Power to Redefine Your Health 15

RECIPES

Salatet Malfouf (Lebanese Cabbage Salad)

A simple cabbage salad made with lemon juice, olive oil, garlic, and mint.

Servings: 4
Total Time: 15 minutes

INGREDIENTS

½ medium head of cabbage, thinly sliced
1 medium clove garlic, minced
2 Tbsp. fresh lemon juice
2 Tbsp. olive oil
¼ tsp. salt
2 Tbsp. chopped fresh dried mint leaves

INSTRUCTIONS

- In a large bowl mix the garlic, lemon juice, olive oil, salt, and mint until thoroughly combined.
- Add the shredded cabbage to the bowl and toss to coat.
- Let the salad sit at room temperature for 10 minutes to allow flavors to meld or cover and refrigerate to allow the flavors to meld a little more and serve at later time. Served room temperature or cold, it's a tasty salad either way.

NOTES & TIPS

Drying out fresh mint leaves:

[figure not shown]
- Separate the leaves from the stems and lay on a microwave safe plate in a single layer. Cook for 10 second intervals until mint begins to curl. Should only take about 30 seconds to dry.

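### For cruciferae intake, the sufficient-power conclusion depends on a baseline of 33-34 g/day; at the plan's own 52.7 g/day and minimum goal of 75 g/day, power is about 43%

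*Combined protocol and SAP*

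**What the plan says.** All of the power argument is in Section 19, Sample Size Determination, patient paragraph.

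- With 40 per arm, ANCOVA and R² = 0.2 between baseline and post-intervention values, the plan claims 80% power for 0.57 within-group SDs. The intake SD, from Be-Well, is "62 g/day for cruciferae intake", so the detectable difference is "35.3 g/day of cruciferae intake between groups".
- The intake goal is to raise "cruciferae intake from the baseline of 52.7 gram (0.7 serving) to at least 75 gram (a typical serving size") by 6 months. The starting value is also from Be-Well; Section 2 reports that "daily intake of cruciferae was about 52.7 gram, or approximately 0.7 servings".
- The closing sentence opens with its premise, "Given the generally lower cruciferae intake observed in other BCS studies (around 0.44-0.45 serving, equivalent to 33-34 gram per day"), and ends with "the proposed study will have sufficient power to detect our projected differences".

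Section 10, Table 1, gives the "Program goal of 1 serving of cruciferae per day", which matches the 75 g serving in Section 19. Section 19, Primary Analysis, treats a significantly positive group coefficient as the sign that the intervention raises intake.

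**The concern.** Three consecutive sentences do not fit together unless the baseline changes between them. The minimum gain from the stated baseline is 75 − 52.7 = 22.3 g/day, which is smaller than the 35.3 g/day the trial can detect with 80% power. The last sentence reaches sufficiency by taking the mean from other survivor studies and keeping the SD from Be-Well. It does not say what power is if patients eat as the Be-Well cohort did, nor which baseline the trial is planned on. Nothing in eligibility secures the lower one, because Section 11 deliberately does not screen on current intake.

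Intake is one of two primary outcomes. If mean baseline is near 52.7 g/day and the intervention arm averages 75 g/day, a non-significant intake result is more likely than not. A reader who relies on the power statement could then take that result as evidence that the programme failed to change diet.

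**Working it through.** **Inputs (Section 19).** n = 40 per arm, 1:1; two-sided α = 0.05; R² = 0.2; SD 62 g/day (intake) and 8.9 µM (ITC). The documents give no expected control-arm change and no dropout rate; both are set to zero here as an assumption.

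**Method.** ANCOVA with one baseline covariate:

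- residual SD = SD × √(1 − R²)
- SE of the between-group difference = residual SD × √(2/40)
- df = 2 × 40 − 3 = 77; critical t = 1.991
- power from the noncentral t with noncentrality difference/SE

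For intake, SE = 62 × √0.8 × √(2/40) = 12.4 g/day. For ITC, SE = 8.9 × √0.8 × √(2/40) = 1.78 µM.

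**The plan's own figure.** Solving for 80% power gives 0.567 SD, which rounds to the plan's 0.57. Then 0.57 × 62 = 35.3 g/day and 0.57 × 8.9 = 5.1 µM. The plan's calculation is reproduced.

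**Serving conversion.** 52.7/75 = 0.70 serving, and 0.44 to 0.45 × 75 = 33.0 to 33.8 g. The conversions are consistent.

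**Power for the projected differences.**

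| Scenario | Difference | Difference/SE | Power |
|---|---|---|---|
| Intake 52.7 to 75 g/day | 22.3 g | 1.80 | 43% |
| Intake 52.7 to 80 g/day | 27.3 g | 2.20 | 58% |
| Intake 52.7 to 85 g/day | 32.3 g | 2.60 | 73% |
| Intake 45 to 75 g/day | 30 g | 2.42 | 67% |
| Intake 34 to 75 g/day | 41 g | 3.31 | 90% |
| Intake 33 to 75 g/day | 42 g | 3.39 | 92% |
| ITC 4.4 to 10 µM | 5.6 µM | 3.15 | 87% |

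**Break-even values.** The 80% difference is 0.5674 × 62 = 35.2 g/day. Reaching 75 g/day therefore needs a mean baseline of 75 − 35.2 = 39.8 g/day or less. From 52.7 g/day the intervention arm would need a mean of 52.7 + 35.2 = 87.9 g/day.

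**Sensitivity to the SD (values other than 62 g are assumptions).** The break-even baseline is 75 − 31.2 = 43.8 g/day at SD 55, and 75 − 28.4 = 46.6 g/day at SD 50. If the SD scales with the mean (CV 62/52.7), it is 45.0 g/day. All are below 52.7. A gain of 22.3 g/day reaches 80% only if the SD is about 22.3/0.5674 = 39.3 g/day or less.

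**Sensitivity to the favourable assumptions (illustrative).** A 5 g/day rise in controls reduces the differences to 17.3 and 36-37 g/day, with power of 28% and 82-84%. With 36 or 32 analysed per arm and no control change, power is 39% or 35% at 22.3 g/day, and 87-89% or 83-85% at 41-42 g/day.

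**Precision.** The expected 95% CI half-width for the between-group intake difference is 1.991 × 12.4 = 24.7 g/day.

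**The case against.** A reader might infer that the plan claims sufficient power without any condition. It does not: the premise of lower intake is in the same sentence. Section 11 relies on the same 0.44-0.45 servings to justify not screening on intake. Preferring those figures is arguable, since Section 2 describes the Be-Well patients as newly diagnosed and this trial enrols survivors. At 33-34 g/day the statement is correct. A careful reader can also subtract 52.7 from 75 and see that the result is below 35.3.

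A second tempting reading is that the trial has a 43% chance of success on intake. The documents do not support that either. The goal is a floor, and the magazine in Appendix P asks each participant for at least one serving a day. Intake with an SD above its mean is right-skewed, so some participants probably already exceed 75 g. If everyone below 75 g rose to 75 g and the rest stayed put, the arm mean would be 75 × P(X ≤ 75) plus the contribution from those above. That comes to about 88 g/day for a lognormal distribution with mean 52.7 and SD 62, or about 91 g/day for a gamma. Those distributions and full adherence are assumptions; 60% adherence under the lognormal gives 52.7 + 0.6 × (88 − 52.7) ≈ 74 g/day. Appendix P also tells participants "One serving size is 1 cup at the time you eat it", raw or cooked, whereas Section 2 equates a serving to half a cup when cooked. The two definitions need reconciling, and the Appendix P one could take intake above 75 g.

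Finally, this is a pilot, no stated go/no-go decision depends on intake significance, and ITC is adequately powered.

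All of this limits the point without removing it. The clause gives a reason for expecting a larger gain; it does not give the power if that reason fails. The lower figures come from a pilot of 48 survivors and a retrospective study of 239 patients, against over 1,400 in Be-Well, which the plan itself uses for the goal's starting value and the SD. A mean near 88 g/day is nowhere stated as the projection. Pilot status does not make a power statement true at a baseline where it fails.

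**Conclusion.** Wrong as written for cruciferae intake, with modest severity. The detectable difference is correctly calculated, and the lower baseline is disclosed. The sufficiency conclusion does not hold for a mean rise from the plan's own 52.7 g/day to the 75 g/day minimum, where the chance of a non-significant result is about 57%. It does hold from 33-34 g/day, and it holds for urinary ITC.

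These figures assume 40 analysed per arm, SD 62 g/day, R² = 0.2 and no control-arm change. Dropout, or a rise in intake under the active control programme, would lower every intake figure. Neither end of the range is a forecast: the Be-Well values come from a preliminary food-frequency analysis, and this trial measures intake with an adapted cruciferae questionnaire (Section 8).

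**What to change.** Replace the last sentence of the patient paragraph with wording such as:

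> With 40 analysed per arm, SD 62 g/day, R² = 0.2 and no control-arm change, power to detect a rise in mean intake to the minimum goal of 75 g/day is about 43% if mean baseline intake is 52.7 g/day (Be-Well) and about 90-92% if it is 33-34 g/day (other BCS studies); 80% power requires a mean baseline of about 40 g/day or less. Power for urinary ITC (4.4 to 10 µM) is about 87%.

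Then state which baseline is the planning baseline and why.

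Add to Primary Analysis that the ANCOVA between-group difference in intake will be reported with its 95% confidence interval. The opening paragraph of Section 19 attaches its intervals to the pre-post changes in both arms and does not clearly promise one for this contrast. With an expected half-width of about 24.7 g/day, the interval would show whether a non-significant result still leaves room for the 22.3 g/day gain.

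The cost is a few sentences and one interval from a model already planned, with no extra patients, data or design change. The downside is that the stated power for intake becomes conditional and less favourable.
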